# 5. Investigational Plan

# 5.1. Study Design

This will be a single clinical study conducted in 2 parts. The duration of study participation will be approximately 37 days for part 1, including a 30-day screening period, a 4-day treatment period (Days 1-4) and subjects leaving the clinic on the morning of Day 7 following completion of scheduled End-of-Study activities. For part 2, the duration of participation will be approximately 51 days, including a 30-day screening period, a 4-day treatment period (Days 1-4) and subjects leaving the clinic on the morning of Day 7. Subjects in part 2 will then return to the clinical for follow-up visits on Days 10, 14 and 21 after which End-of-Study activities will be completed.

#### 5.1.1 Part 1

Part 1 is an open-label, randomized, 4-arm pilot study to evaluate the effects of multiple applications of 4 different topical sunscreen formulations in healthy adult subjects. Each arm will include 6 subjects (3 male and 3 female) with 1 formulation. A total of 24 subjects (12 male and 12 female) from all 4 arms will be admitted to the clinical research unit (CRU) on Day 0.

On the morning of Days 1 through 4, subjects will receive a topical application of the study product at approximately 0900 hours. The study drug will be weighed in advance and applied by a qualified person from the study team. Subjects will then receive 3 more topical applications on the same day at 2, 4, and 6 hours after the first dose.

### 5.1.2 Part 2

Part 2 is an open-label, 4-arm-study to evaluate the pharmacokinetics of avobenzone, oxybenzone, octocrylene, homosalate, octisalate and octinoxate (Part 2 products will not contain ecamsule) after multiple applications of a topical sunscreen formulation in healthy adult subjects. Part 2 will include 48 subjects (24 male and 24 female) and 12 subjects in each arm (6 male and 6 female). One of the formulations in Part 2 will be selected based on the plasma exposure data from the pilot study (Part 1). In addition, 3 new formulations will be added.

On the morning of Days 1 through 4, subjects will receive a topical application of the study product at approximately 0900 hours. The study drug will be weighed in advance and applied by a qualified person from the study team. Subjects will only receive one application on Day 1. On Days 2, 3 and 4, subjects will receive an initial dose and 3 more topical applications on the same day at 2, 4, and 6 hours after the first dose.

# 5.1.3 Tape Stripping

For Part 2 only, skin tape stripping (6 consecutive strippings) of the lower back (area: around 3.8 cm^2) will be conducted once on Days 7 and 14 to determine residual sunscreen active ingredients in the superficial layers of the skin. The intention of the stripping is to determine the concentration of sunscreen active ingredients in superficial layers to estimate the potential skin deposit and 6-8 strips will be required to remove most of the stratum corneum layer [2-3]. The number of strips is restricted to 6 to minimize any skin irritation or skin rash [2-3].

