# 5.7.1.2 Tape Stripping Sample Collection

For Part 2 only, tape stripping of the lower back to an area of around 3.8 cm^2 will be conducted once on Days 7 and 14 to determine residual sunscreen active ingredients in the superficial layers of the skin. Tape stripping will be applied to different areas of the lower back on Day 7 vs. Day 14 to prevent false sampling.

The area on the lower back for each subject will be marked with a skin marker. Before executing the tape stripping, hair on the marked area will be removed with the 3M trimmer (no razors as this would damage the skin and could lead to false sampling). A pre-weighed standard tape (Standard D-Squame ® adhesive tape) will be applied to a marked area under constant pressure of 225 g/cm^2 for 5 seconds using a D-Squame ®

Pressure device. The tape will be removed swiftly and placed in a standard tape rack after weighing. Tape stripping will be performed 6 additional consecutive times in the same area with sampling intervals of  $1 \pm 0.5$  minutes.

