# 5.7.1.3 Pharmacokinetic Specimen Handling

The PK blood samples (10 mL each) will be collected into tubes containing K2EDTA, inverted several times to mix the blood with the anticoagulant, and placed in an ice bath. Within 30 minutes of collection, the samples will be centrifuged for 10 minutes, at 3000 revolutions per minute, at 4°C, by a study team member.

The plasma will be separated using a disposable plastic pipette and approximately half of the plasma will be transferred into duplicate cryotube vials labeled as Aliquot A (primary) and Aliquot B (backup). The plasma samples will be appropriately labeled and stored frozen at  $-70^{\circ}$ C or below until shipment. Temperature monitoring logs should be maintained and accessible for review by the study monitor.

The Aliquot A samples (primary) will be shipped first, on dry ice, to the bioanalytical laboratory at FDA for processing when requested by the sponsor. The Aliquot B samples (backup) will be held for a second shipment at a time after the completion of all Aliquot A sample shipment(s) and the timing of the Aliquot B shipment communicated by the sponsor. None of the PK blood samples will be stored at clinical facility for future use, however the sponsor will store them for analytical purposes of this study only.

The tape strips will be transferred to pre-labeled D Squame  $\mathbb{R}$  standard storage cards and stored frozen at  $-70^{\circ}$ C or below until shipment.

Both plasma and skin concentrations of avobenzone, oxybenzone, ecamsule, octocrylene, homosalate, octisalate and octinoxate (where applicable) will be assayed using a validated liquid chromatography with tandem mass spectrometry method.

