### Across all study days (Primary Endpoint)

• Maximum concentration (observed peak drug concentration) (Cmax)

#### Days 1

- Maximum concentration (observed peak drug concentration) (Cmax)
- Time at which  $C_{max}$  occurs  $(T_{max})$

• AUC from time 0 to the sampling time corresponding to the last quantifiable concentration (Clast) (AUC0-t), calculated by the mixed linear logarithmic trapezoidal method

### Days 2 and 3

- Residual drug concentration (predose level) (Ctrough)
- 3 h post dose concentration

### Day 4

- Elimination rate constant (Kel), obtained by linear regression of the log-linear terminal phase of the concentration-time profile using at least 3 data points, excluding Cmax, otherwise Kel will not be determined. The acceptability criteria for determination of Kel will be a coefficient of regression more than or equal to 0.98.
   When Kel will not be determined, AUC0-inf and t1/2 will not be reported.
- Terminal half-life  $(t_{1/2})$ , calculated using the equation  $\ln 2/k$  after the last study drug application (on Day 4)
- Accumulation ratios, calculated using the following formula:

$$R_1 = AUC_{0-23} Day 4 / AUC_{0-23} Day 1$$

• AUC from time 0 extrapolated to infinity (AUC0-inf), calculated by the mixed linear-logarithmic trapezoidal method as:

$$AUC_{0\text{-inf}} = AUC_{0\text{-t}} + C_{last} / K_{el}$$

When the extrapolation represents more than 20%,  $AUC_{0-inf}$  and  $t_{1/2}$  will not be reported.

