### 5.9.3 General Statistical Considerations

All data will be presented in data listings. Data from subjects excluded from an analysis population will be presented in the data listings but not included in the calculation of summary statistics.

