## 5.9.6 Pharmacokinetic Analyses

Plasma concentrations and PK parameters of avobenzone, oxybenzone, octocrylene, ecamsule, homosalate, octisalate and octinoxate (where applicable) will be listed and summarized using descriptive statistics (n, arithmetic mean, SD, minimum, median, and maximum) by nominal PK sampling time.

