All data will be presented in data listings. Data from subjects excluded from an analysis population will be presented in the data listings but not included in the calculation of summary statistics. The number of subjects who enroll in the study and the number and percentage of subjects who complete each assessment will be presented. The frequency and percentage of subjects who withdraw or discontinue from the study and the reason for withdrawal or discontinuation will be summarized. Continuous demographic and baseline characteristic variables (age, height, weight, body mass index) will be summarized overall and by treatment using descriptive statistics (number of subjects, mean, standard deviation [SD], median, interquartile range [IQR], and minimum and maximum). The number and percentage of subjects in each class of categorical demographic and baseline characteristic variables will also be summarized.

5 Pharmacokinetic (PK) Analyses and Primary/Secondary Outcomes

The PK sampling schedule for this study is summarized in Appendix A. The following PK parameters will be determined for each subject in Part 1 and Part 2:

Across all study days

- Maximum concentration (observed peak drug concentration) (C_{\max})

Day 1

- Maximum concentration (observed peak drug concentration) (C_{\max})
- Time at which C_{\max} occurs (T_{\max})
- AUC from time 0 to the 23 hour time point (C_{last}) (AUC_{0-23})

Days 2 and 3

- Residual drug concentration (predose level) (C_{trough})
- Concentration 3 hours after the last dose of the day

Day 4

- Maximum concentration (observed peak drug concentration) (C_{\max})
- Time at which C_{\max} occurs (T_{\max})
- Elimination rate constant (K_{el}) and terminal half-life ($t_{1/2}$); calculated after final dose using all the available data up to last study sample (144 hours for Part 1; 432 hours for Part 2)
- AUC from time 71 to the 95 hour time point (AUC_{73-95})
- AUC from time 0 extrapolated to infinity ($AUC_{0-\text{inf}}$) and/or last observed time point

Day 5, 6, 7, 10 (Part 2 only), 14 (Part 2 only) and 21 (Part 2 only)

- Residual drug concentration (C_{trough})

The primary and secondary outcomes of this study are as follows:

Primary Outcome:

1. Maximum* Avobenzone concentration (C_{\max})

Secondary Outcomes:

1. Maximum* Oxybenzone concentration (C_{\max})
2. Maximum* Octocrylene concentration (C_{\max})
3. Maximum* Ecamsule concentration (C_{\max})
4. Maximum* Homosalate concentration (C_{\max})

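### Part 2 tape strips are collected to estimate a skin deposit but have no planned analysis, and the terminal plasma slope is called an elimination rate constant that plasma data alone cannot establish

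*Protocol*

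**What the plan says.** **Strips.** Protocol 5.1.3 gives their purpose: "The intention of the stripping is to determine the concentration of sunscreen active ingredients in superficial layers to estimate the potential skin deposit". The stripping "will be conducted once on Days 7 and 14 to determine residual sunscreen active ingredients in the superficial layers of the skin". Protocol 5.7.1.3 confirms measurement: "Both plasma and skin concentrations of avobenzone, oxybenzone, ecamsule, octocrylene, homosalate, octisalate and octinoxate (where applicable) will be assayed".

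**Analysis.** The parameter list in Protocol 5.7.1.4 contains plasma quantities only. Protocol 5.9.6 states: "Plasma concentrations and PK parameters of avobenzone, oxybenzone, octocrylene, ecamsule, homosalate, octisalate and octinoxate (where applicable) will be listed and summarized". Skin concentrations are not named. SAP Section 5 lists plasma parameters, and its primary and secondary outcomes are all Cmax. The SAP text supplied does not mention tape strips or skin concentrations. The one rule that covers them is general (Protocol 5.9.3, repeated in SAP Section 4): "All data will be presented in data listings".

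**Terminal slope.** Protocol 5.7.1.4 names Kel the elimination rate constant and defines it as "obtained by linear regression of the log-linear terminal phase of the concentration-time profile using at least 3 data points", with a regression coefficient of at least 0.98. SAP Section 5 keeps the name for Kel and says that Kel and t1/2 are "calculated after final dose using all the available data up to last study sample", by non-compartmental methods. In both documents t1/2 is the terminal half-life. The synopsis lists no reference treatment.

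**The concern.** Part 2's primary objective covers both pharmacokinetics and systemic absorption. A slow late decline in plasma has at least two explanations: the body clears the ingredient slowly, or the skin keeps supplying it after application stops. These are different answers to that objective. The protocol takes the second seriously enough to collect strips for it, and it warns subjects of pain, irritation and rash from the procedure.

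Followed as written, the plan lists the strip results without estimating any deposit, and it prints an elimination label on Kel whichever process sets the slope. Neither document cautions that the slope may reflect release from skin. If the comparison is not specified in advance, any later use of the strips to explain a long half-life will be post hoc.

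**Working it through.** The documents state no calculation on this point, so there is no figure to reproduce. The check asks whether the scheduled plasma data can identify the limiting process, and whether the strips could.

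**Inputs from the documents (Part 2).**
- Applications: one on Day 1, then four a day at 0, 2, 4 and 6 h on Days 2 to 4. That is 1 + 3 × 4 = 13, the last at 78 h.
- Plasma: protocol schedule to 480 h, including 144 h (Day 7) and 312 h (Day 14).
- Strips: Days 7 and 14, with no clock time given; taken as 168 h apart.
- Arms: 12 subjects each.

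**Assumptions.** The documents give no half-lives. I took a slow process of 24, 48, 72 or 120 h and a fast one of 4 or 8 h. The model has one compartment with first-order release (ka) and elimination (ke). Showering, assay limits and noise are ignored.

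**Step 1: plasma.** After one application,

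C(t) ∝ ka × [exp(−ke·t) − exp(−ka·t)] / (ka − ke).

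Exchanging ka and ke leaves the fraction unchanged. Only the multiplier ka changes, and it cannot be told apart from the unknown absorbed fraction and volume. Summing over 13 applications preserves this. Numerically, the normalised profiles differ by less than 1e-15 at every scheduled time.

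Log-linear fit to samples from 95 h onward:

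| Slow half-life (h) | Fitted half-life, release slow (h) | Fitted half-life, elimination slow (h) |
|---|---|---|
| 24 | 24.0–24.3 | 24.0–24.3 |
| 48 | 48.1–48.6 | 48.1–48.6 |
| 72 | 72.2–73.1 | 72.2–73.1 |
| 120 | 120.4–122.5 | 120.4–122.5 |

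R-squared is at least 0.9987 in every row, so the 0.98 rule passes either way. Extrapolation is at most 8.9%, so the protocol's 20% rule does not intervene either.

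**Step 2: skin.** The Day 14/Day 7 ratio is 2^(−168/skin half-life).
- Release slow: 2^(−168/24) = 0.8%; 2^(−168/48) = 8.8%; 2^(−168/72) = 19.8%; 2^(−168/120) = 37.9%. In the same model the 312 h/144 h plasma ratio nearly matches (8.8% to 8.9% for 48 h).
- Elimination slow, skin half-life 8 h: 2^(−168/8) = 2^(−21) = 4.8e-7, while the plasma ratio is the same as above. The modelled skin amount on Day 7 is at most 0.012 of one application, against 0.97 to 7.5 applications when release is slow.

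**Step 3: precision.** The 95% limits on a geometric mean ratio are ×/÷ exp(2.201 × SD/√12). For an assumed SD of the log ratio of 0.3, this is exp(0.191) = 1.21; for 0.8, exp(0.508) = 1.66. That resolves the contrasts in Step 2 but not close half-lives: 48 h against 60 h gives 0.088 against 0.144, a 1.63-fold difference, inside ×/÷ 1.66.

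**Step 4: strip count.** Protocol 5.1.3 specifies six consecutive strips. Protocol 5.7.1.2 describes one strip and then six more, which makes seven. A total per cm² depends on which applies.

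**The case against.** **Naming and consequence.** Only Kel carries the elimination label; t1/2, which readers will use most, is already called terminal. Nothing in the documents says a long t1/2 will be read as slow elimination. The trial is exploratory, its size is empirical, and slow release does not bias an observed Cmax. All of this stands, and it limits the point to Kel and to the interpretation of persistence.

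**A reader might infer that the trial cannot tell the two explanations apart.** The documents do not support that. The strips are taken, assayed and listed, so the limitation belongs to the planned analysis and can be repaired in Part 2.

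**A reader might also infer that a skin decline faster than plasma proves elimination is the slow step.** It does not. Strips sample superficial layers, and Protocol 5.1.3 itself expects 6 to 8 of them to remove most, not all, of the stratum corneum. A deeper reservoir could still feed plasma.

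**A reader might see day confounded with site, because** "Tape stripping will be applied to different areas of the lower back on Day 7 vs. Day 14". Protocol 5.7.1.2 does this deliberately, within one region, to prevent false sampling. It does not fix the same area for everyone on Day 7, and no site effect is quantified, so confounding is not established.

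**Undefined ratios.** If skin empties quickly, Day 14 values may fall below quantification. With a 12 h skin half-life, Day 14 is (312 − 78)/12 = 19.5 half-lives after the last application. No assay limit is stated and missing data are not imputed, so a ratio alone would fail in just this case. This stands, and the summary must count such values.

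**Conclusion.** The point holds as a gap in the planned Part 2 analysis. The strips' stated purpose has no corresponding summary, and Kel carries a label that plasma data alone cannot support.

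That plasma cannot discriminate is exact within the linear first-order model and does not depend on the half-lives chosen. How well the strips would discriminate does depend on assumed half-lives and SDs: separation is by orders of magnitude when the two processes differ widely, and poor when candidate half-lives are close. The comparison is supportive, not decisive, because it has two time points and superficial layers only. Part 1 has no strips. Primary and secondary Cmax outcomes are untouched. The change should be made, but the main result does not depend on it.

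**What to change.** 1. In SAP Section 5, for Part 2, add one descriptive table by arm and ingredient:
   - skin amount per cm² on Days 7 and 14;
   - number of subjects below quantification on each day;
   - within-subject Day 14/Day 7 skin ratio where both values are quantifiable;
   - beside it, the within-subject 312 h/144 h plasma ratio, with 95% limits on both ratios.
2. State the reading in advance. A similar decline in skin and plasma supports release-limited kinetics. A faster skin decline is not proof of elimination, because deeper skin is not sampled.
3. Relabel Kel in both documents as the apparent terminal rate constant; leave t1/2 as terminal half-life.
4. Before computing totals, reconcile the strip count between Protocol 5.1.3 and 5.7.1.2. Also reconcile the last Part 2 sample used for Kel: SAP Section 5 says 432 h, SAP Attachment A says 480 h.

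Cost: one extra table, one changed label and two reconciled passages, with no new samples or visits. The downside is a table that supports only limited inference.

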#### 5.1.4 Common Procedures

Details of study visits and study procedures are described in Section 5.6 and Section 5.7, respectively, and the overall Schedule of Events for both parts of the study is presented in Section 10.1.

In both parts of the study, approximately 2 mg of sunscreen per 1 cm² of body surface (calculation per method of Dubois) will be evenly applied 4 times per study day (except for a one-time application on the first day in part 2) to areas of the body typically exposed to the sun: face, ears, neck, torso, arms, and legs (approximately 75% of the body surface area). The antecubital areas will be avoided when applying the sunscreen due to potential contamination of the sites used for intravenous (IV) PK blood sample collection. The topical applications of the study drug will be administered with subjects in swim wear to simulate real world settings as well as for easy application. In addition to swim wear, subjects may wear scrubs in between applications and at other times throughout the day/night. Subjects are required to shower each morning after the first PK blood sample collection (and before the first sunscreen application for that day), but not at other times during the day. And, subjects should not use any personal care products which contain avobenzone, oxybenzone, ecamsule, octocrylene, homosalate, octisalate or octinoxate during the study.

Blood samples (approximately 10 mL per sample) will be collected for determination of avobenzone, oxybenzone, octocrylene, ecamsule, homosalate, octisalate and octinoxate (where applicable) plasma concentrations.

Safety evaluations will include adverse event (AE) monitoring, vital sign measurements, and physical examinations. All AEs reported by the subject or observed by the investigator or CRU staff will be recorded. Any AE reported after the informed consent is signed and before study drug application will be recorded as medical history.

Subjects will remain in the CRU after admission on Day 0 until discharge on the morning of Day 7. In Part 2, subjects will return to the clinic on Day 10, 14 and 21 for follow-up PK sampling (Days 10, 14 and 21) and tape stripping (Days 14).

Subjects are not allowed to use products containing any of the active ingredients from 7 days before check-in until completion of End-of-Study procedures.

#### 5.1.5 Risk/Benefit

Subjects will be informed that participation in a human PK study like the present one cannot be of benefit to healthy volunteers. Nevertheless, the information from the physical examination, vital sign measurements, and ECG results may be shared with the subject's personal physician if this is the subject's choice. Subjects will be informed that

it is also their choice to inform their personal physician that they are participating in this research study.

Subjects will be informed that their contribution to the study is of major importance to agencies like the U.S. FDA for helping this agency better evaluate the effects of human systemic absorption of sunscreen ingredients. However, since this is a study involving healthy volunteers, subjects will be informed that they have the alternative not to participate.

Subjects will be informed that they may be exposed to risks associated with the pharmacological properties of the study drugs and the study procedures.

The study sunscreen products will not be administered to anyone who is pregnant. All women must take a pregnancy test before receiving any study drug in this study. All men and all women of childbearing potential enrolled in this study will be informed that they must use 2 highly effective birth control methods (as determined by the investigator or designee; one of the methods must be a barrier technique) during the study and for at least 1 month after the last application of study drug. Subjects will be informed that they must notify the investigator if they or their female partners become pregnant during the course of the study.

Subjects will be informed that insertion of an IV catheter may be required for blood sample collection on Days 1 and 4 and, during insertion of the catheter, soreness, bruising, or infection at the insertion site are possible but unlikely. Subjects will also be informed that dizziness and lightheadedness may occur during direct venipuncture, insertion of the IV catheter, or during blood collection.

Subjects will be informed that tape stripping applied to the skin may cause mild pain or irritation and skin rash at the area of tape stripping after the procedure.

Subjects will be informed that they may eat only meals and snacks that are provided during periods of their stay in the study clinic, and that they must consume all of each meal that is served at a reasonable pace (within 25 minutes).

Subjects will be informed that the confidentiality of their data will be respected at all times according to state law, and the study personnel handling their study data are bound by confidentiality agreements.

Subjects will be informed that the study drug and all tests, procedures, and visits required by the study are provided at no cost to them. If subjects become ill or physically injured because of participation in this study, they will be informed that costs of treatment will not be covered by the sponsor.

If a subject becomes pregnant, she will be informed that neither Spaulding Clinical Research nor the sponsor will be responsible for the cost of any obstetric or related care, or for the child's care.

Subjects will be informed by the Investigator of significant new findings that may develop during the course of this research study that may relate to their willingness to continue participation in the study.

